2. STUDY OBJECTIVES, ENDPOINTS AND HYPOTHESES

2.1. Objectives

Primary Objective:

The primary objective of this study is to estimate the incidence rate (percentage) of eyes with clinically significant slit-lamp findings (Grade 3 or 4) related to each study lens (Test lens and Control lens) after approximately 2-weeks of lens wear.

Exploratory Objectives:

The exploratory objectives of this study include the estimation of the mean difference between study lenses (Test lens and Control lens) with respect to distance monocular high luminance, high contrast (HLHC), logMAR visual acuity (at the 1-week follow-up visit), and CLUE comfort, vision, and handling scores (at the fitting, 1- and 2-week follow-up visits). Additional exploratory objectives of the study are to estimate the mean and standard deviation of the settled toric roation of each study lens (Test lens and Control lens) following lens settling and after 1- and 2-weeks of lens wear, and to assess the toric lens orientation of each study lens, 1- and 3-minutes after lens insertion. Adverse events will also be monitored and collected.

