14.7. Exploratory Analyses

Summary for exploratory endpoints will be provided for both the ITT and the Per-Protocol populations. However, all analyses for exploratory endpoints will be conducted on the ITT population.

Distance Monocular HLHC logMAR visual acuity

Distance monocular HLHC logMAR visual acuity at the 1-week follow-up will be summaried and presented only descriptively by lens type accompanied with the 2-sided 95% CIs. Summary statistics are described in section 14.1.

CLUE Comfort, Vision, and Handling Scores

The analysis of exploratory endpoints of CLUE comfort, vision and handling at the fitting, 1-, and 2-week follow-up visits will be conducted separately for each CLUE domain. The exploratory analysis of each CLUE score endpoints will include the estimation of mean CLUE scores and associated 95% CIs for each study lens (Test lens and Control lens). Additionally, the mean difference between the Test and Control lens paired with the 95% CI will be calculated.

CLUE scores will be analyzed using a linear mixed model, adjusting for baseline scores as a covariate. Sequence of lens wear, study period, lens type (Test and Control), timepoint (fitting, 1-week, and 2-week follow-up visit), and the ineraction lens type by timepoint will be included as fixed effects. Other baseline characteristics such age, gender, and/or race will be included as fixed covariates when appropriate. Site and subject nested within site will be included as random effects (G-side). Residual errors from measurements within the same subject and timepoint across study period will be modeled using an unstructured covariance structure (UN). If the model does not converge, other covariance structures will be considered. The Kenward and Roger method will be used for the denominator degree of freedom. Estimates for each study lens and between study lenses (Test lens and Control lens) will be carried out using two-sided 95% CIs for the least-square mean and/or mean difference.

Toric Lens Orientation

The distribution (counts, percentages) of eyes for the toric Orientation (in degrees) at 1- and 3-minutes after lens insertion will be summarized by timepoint (fitting, 1-, and 2-week follow-up) and lens type.

Mean Settled Lens Orientation

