Mean settled lens orientation will be summarized separately for each timepoint (fitting, 1-, and 2-week follow-up visits) and lens type (Test and Control). Mean settled lens orientation is calculated by eye by averaging across all lens orientation measurements collected at least 15-minutes after lens insertion. The standard deviation of average settled lens orientation will also be calculated.

The exploratory analysis of this exploratory endpoint will include the estimation of the mean settled rotation by study lens paired with the corresponding two-sided 95% CIs for each lens, and the point estimate with the two-sided 95% CI for the mean difference.

Mean settled rotation will be analyzed using a linear mixed model. Sequence of lens wear, period, lens type, and first order carryover effect will be included in the model as fixed effects. Other baseline characteristics may be included, such as, race and age. Subject will be included as a random effect. Residual errors between measurements within a subject across periods will be modeled using an unstructured (UN) covariance structure. The Kenward and Roger Method will be used for the calculation of denominator degrees of freedom. Estimates will be calculated using two-sided 95% confidence intervals constructed for the least-square mean and/or least-square mean difference.

Adverse Events

All Adverse Events reported during this study will be provided in a listing. This listing will include subject demographic information, treatment information (associated with the time of the reported AE), AE type (ocular or non-ocular), seriousness / classification, causality or relatedness, adverse event severity, outcome, actions taken and the associated start and end date / time for each AE.

Additional exploratory analyses may be considered at the discretion of the study sponsor.

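### Both mixed models in 14.7 index the residual covariance by period rather than by lens, so the per-lens 95% CIs are mis-sized if the two lenses differ in spread (minor; exploratory endpoints only)

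*Combined protocol and SAP*

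**What the plan says.** Section 14.7 plans two linear mixed models.

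- **Mean settled lens orientation.** Fixed effects are sequence, period, lens type and first-order carryover. "Subject will be included as a random effect". For the residuals, "Residual errors between measurements within a subject across periods will be modeled using an unstructured (UN) covariance structure". The outputs include "estimation of the mean settled rotation by study lens paired with the corresponding two-sided 95% CIs for each lens", and also the mean difference with its CI.
- **CLUE comfort, vision and handling.** Fixed effects are baseline score, sequence, period, lens type, timepoint and lens by timepoint. "Site and subject nested within site will be included as random effects (G-side"). For the residuals, "Residual errors from measurements within the same subject and timepoint across study period will be modeled using an unstructured covariance structure (UN"). The outputs include "estimation of mean CLUE scores and associated 95% CIs for each study lens (Test lens and Control lens"), and also the mean difference with its CI. There is one fallback: "If the model does not converge, other covariance structures will be considered".

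Neither model has a residual variance that depends on lens type, and the random effects are common to both lenses. Section 2.1 sets as an exploratory objective to "estimate the mean and standard deviation of the settled toric roation of each study lens". Section 2.3 states that no hypotheses are tested.

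**The concern.** Under Test/Control and Control/Test sequences, period 1 holds Test values from one sequence and Control values from the other, and period 2 holds the reverse. A matrix indexed by period can represent a change in spread over time. It cannot represent a difference in spread between the lenses.

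A CI for each lens mean is a named output of both models. If one lens is more variable, its interval would be too short and the other's too long. A report could then show clearly different descriptive SDs by lens next to model CIs of almost equal width. The Kenward-Roger method adjusts for small samples, but it cannot supply a variance that the model does not contain. The CLUE fallback does not help either, because unequal spread does not in itself cause non-convergence.

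**Working it through.** **Inputs from the documents.** Two sequences (4.1); 60 completers from about 66 enrolled at 10% dropout (14.2); CLUE population SD 20 (2.2). The figure of 66 is 60 × 1.1; dividing by 0.9 gives 66.7, or 67, which does not matter here. The documents state no precision figure for the per-lens CIs, so there is none to reproduce.

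**Assumptions.** 30 completers per sequence (n1 = n2 = 30), one value per subject per period, no site effect or covariate. No lens-specific SD is given for either endpoint, so SD ratios from 1.0 to 2.0 are shown.

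**Algebra.** With sequence, period and lens fixed, the four sequence-by-period means are saturated.

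1. LSmean(Test) = ½ × (Test/Control period 1 mean + Control/Test period 2 mean).
2. True variance = sT² × (1/n1 + 1/n2)/4 = sT²/60.
3. Model variance with period indexing = (v1/n1 + v2/n2)/4. Here v1 and v2 are the period variances, each with expectation (sT² + sC²)/2.
4. So the model variance is about (sT² + sC²)/120, for Test and Control alike.
5. With r = larger SD / smaller SD, planned width / correct width = √((1 + r²)/2)/r for the more variable lens and √((1 + r²)/2) for the less variable one. At r = 1.5, √1.625 = 1.275, giving 1.275/1.5 = 0.85 and 1.27.
6. The variance of the Test-Control difference is (v1 + v2 − 2c) × (1/n1 + 1/n2)/4, with c the covariance. Relabelling the two columns in one sequence leaves v1 + v2 and c unchanged, so period and lens indexing give the same difference CI.

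**Simulation.** 40,000 trials per scenario, t with 58 df, within-subject correlation 0.3 and 0.6. Entries are more variable / less variable lens. The half-widths illustrate the CLUE scale with root-mean-square SD 20; period indexing then gives both lenses about 2.00 × 20/√60 = 5.17.

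| SD ratio | Width ÷ correct width | Coverage of nominal 95% CI | Correct half-width |
|---|---|---|---|
| 1.0 | 1.00 / 1.00 | about 95% / 95% | 5.17 / 5.17 |
| 1.1 | 0.96 / 1.05 | about 94% / 96% | 5.41 / 4.92 |
| 1.25 | 0.91 / 1.13 | about 92.7% / 97.4% | 5.71 / 4.57 |
| 1.5 | 0.85 / 1.27 | about 90.8% / 98.7% | 6.08 / 4.05 |
| 2.0 | 0.79 / 1.58 | about 88.3% / 99.8% | 6.54 / 3.27 |

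The simulated period variances averaged about 400 in every row, which confirms step 3. Lens indexing gave 94.8–95.2% for both lenses throughout. The difference CI covered 94.8–95.2% under either indexing.

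**In degrees.** With assumed SDs of 6 and 4 and correlation 0.4, both intervals are 2.63 degrees wide; the correct widths are 3.09 and 2.06. A 33/27 split between sequences gives much the same coverage (90.8% / 98.9%).

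**Carryover check.** The orientation model also has a carryover term. Intercept, sequence, period and lens already use four parameters for four cell means, and carryover would be a fifth. A rank check finds neither the lens LS means nor their difference estimable with all four effects; both are estimable without carryover.

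**The case against.** Much of the case on the other side stands.

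- **The effect is conditional.** No lens-specific SD is given. With equal spreads nothing is wrong, and at a ratio of 1.1 the loss is about one percentage point.
- **Absolute errors are small.** With SDs of 6 and 4 degrees the half-widths are off by (3.09 − 2.63)/2 = 0.23 and (2.63 − 2.06)/2 = 0.28 degrees, while orientation is recorded to the nearest degree. For CLUE at ratio 1.25 they are off by 5.71 − 5.17 = 0.54 and 5.17 − 4.57 = 0.60 points, against the 5-point shift that section 2.2 uses as its reference.
- **The simulated model is simpler than those written.** Orientation is computed by eye, 14.7 does not say how the two eyes enter, and the carryover term must be settled first. The CLUE model has three timepoints, a baseline covariate and a site effect. Site variance enters both lens CIs and dilutes the relative error.
- **No code is given.** Period indexing is the natural reading of both sentences, but it is a reading.

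A reader might infer from the section 2.1 objective that the sponsor expects unequal spread, or that the SD objective is compromised. Neither follows. Planning to report two SDs does not predict that they differ, and the SDs come from descriptive summaries by lens (14.1, 14.7) that do not use this matrix. A reader might also say that the model imposes one pooled variance. It estimates two period variances and a covariance; the difficulty is that each period variance mixes the lenses.

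These points limit the size and the priority. They do not show that the per-lens CIs would be right under unequal spread.

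**Conclusion.** The point holds in a limited form. As written, both models give the two lens means nearly the same standard error whatever the lens spreads. If the spreads differ, the per-lens 95% CI is too narrow for the more variable lens and too wide for the less variable one. Coverage runs from about 94%/96% at an SD ratio of 1.1 to about 88%/99.8% at 2.0, under the assumptions listed, and is correct at 1.0. Which row applies cannot be known from the documents.

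For CLUE the point applies directly, somewhat diluted by the site effect. For orientation it applies once the carryover term and the two eyes have been dealt with.

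A reader might infer that the Test-Control comparison or the safety conclusion is at risk. The documents do not support that: the difference CI is the same under either indexing, and the primary analysis (14.5) is a tabulation of slit-lamp grades that uses neither model. This is a minor, nearly free improvement to exploratory estimates.

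**What to change.** In 14.7, index the unstructured residual matrix by lens type within subject for orientation, and by lens type within subject and timepoint for CLUE. It then holds one variance for Test, one for Control and their covariance. Any other specification that allows lens-specific residual variances would also serve. Keep period as a fixed effect in both models.

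The cost is one phrase per model. The matrix has three covariance parameters before and after, no new data are needed, and nothing is lost if the spreads are equal. There is a small downside: if variance differs by period and the sequences are unequal in size, per-lens coverage moves by about one percentage point (roughly 94–96% at a 33/27 split). For orientation, make this change together with the resolution of the carryover term and a statement of how the two eyes enter the model.

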14.8. Interim Analysis

Not applicable.

14.9. Procedure for Handling Missing Data and Drop-Outs

Missing or spurious values will not be imputed. The count of missing values will be included in the summary tables and listings.

14.10. Procedure for Reporting Deviations from Statistical Plan

The analysis will be conducted according to that specified in above sections. There are no known reasons for which it is planned to deviate from these analysis methods. If for any reason a change is made, the change will be documented in the study report along with a justification for the change.

15. DATA HANDLING AND RECORD KEEPING/ARCHIVING

15.1. Electronic Case Report Form/Data Collection

The data for this study will be captured on electronic case report forms (eCRFs) using the Sitero EDC system. An authorized data originator will enter study data into the eCRFs using the EDC system. Data collected on equipment that is not captured in EDC will be formatted to the specification of the JJVC database manager and sent to JJVC for analysis.

No external data sources will be included in this study.

The clinical data will be recorded on dedicated eCRFs specifically designed to match the study procedures for each visit. Only specifically delegated staff can enter data on a CRF. Once completed, the eCRFs will be reviewed for accuracy and completeness and signed by the Investigator. The sponsor or sponsor's representatives will be authorized to gain access to the subject recordation for the purposes of monitoring and auditing the study.

Edit checks, electronic queries, and audit trails are built into the system to ensure accurate and complete data collection. Data will be transmitted from the clinical site to a secure central database as forms are completed or updated, ensuring information accuracy, security, and confidentiality. After the final database lock, the

Investigator will be provided with Individual Patient Profiles (IPP) including the full audit trail on electronic media in PDF format for all of the study data. The IPP must be retained in the study files as a certified copy of the source data for the study.

The content and structure of the eCRFs are compliant with ISO14155:2020.¹

15.2. Subject Record

At a minimum, subject record should be available for the following:

- subject identification
- eligibility
- study identification
- study discussion
- provision of and date of informed consent
- visit dates
- results of safety and efficacy parameters as required by the protocol
- a record of all adverse events
- follow-up of adverse events
- medical history and concomitant medication
- test article receipt/dispensing/return records
- date of study completion
- reason for early discontinuation of test article or withdrawal from the study, if applicable

The subject record is the eCRF or an external record. The author of an entry in the subject record must be identifiable. The first point of entry is considered to be the source record.

Adverse event notes must be reviewed and initialed by the Investigator.

15.3. Trial Registration on ClinicalTrials.gov

This study will be registered on ClinicalTrials.gov by the Sponsor.

16. DATA MANAGEMENT

16.1. Access to Source Data/Document

The Investigator/Institution will permit trial-related monitoring, audits, IEC/IRB review and regulatory inspection(s) by providing direct access to source data/documents. Should the clinical site be contacted for an audit by an IEC/IRB or regulatory authority, JJVC must be contacted and notified in writing within 24 hours.

16.2. Confidentiality of Information

Information concerning the investigational product and patent application processes, scientific data or other pertinent information is confidential and remains the property of JJVC. The Investigator may use this information for the purposes of the study only. It is understood by the Investigator that JJVC will use information developed in this clinical study in connection with the development of the investigational product and therefore may disclose it as required to other clinical investigators and to regulatory agencies. In order to allow the use of the information derived from this clinical study, the Investigator understands that he/she has an obligation to provide complete test results and all data developed during this study to the Sponsor.

16.3. Data Quality Assurance

Steps will be taken to ensure the accuracy and reliability of data, including the selection of qualified investigators and appropriate clinical sites and review of protocol procedures with the Principal Investigator. The Principal

Investigator, in turn, must ensure that all Sub-Investigators and clinical site personnel are familiar with the protocol and all study-specific procedures and have appropriate knowledge of the study article.

Training on case report form completion will be provided to clinical site personnel before the start of the study. The Sponsor will review case report forms for accuracy and completeness remotely during the conduct of the study, during monitoring visits, and after transmission to data management. Any data discrepancies will be resolved with the Investigator or designee, as appropriate.

Quality Assurance representatives from JJVC may visit clinical sites to review data produced during the study and to access compliance with applicable regulations pertaining to the conduct of clinical trials. The clinical sites will provide direct access to study-related source data/documents and reports for the purpose of monitoring and auditing by JJVC and for inspection by local and regulatory authorities.

16.4. Data Monitoring Committee (DMC)

Not applicable.

17. CLINICAL MONITORING

The study monitors will maintain close contact with the Principal Investigator and the Investigator's designated clinical site personnel. The monitor's responsibilities will include:

- Ensuring that the investigation is being conducted according to the protocol, any subsequent versions, and regulatory requirements are maintained.
- Ensuring the rights and wellbeing of subjects are protected.
- Ensuring adequate resources, including facilities, laboratories, equipment, and qualified clinical site personnel.
- Ensuring that protocol deviations are documented with corrective action plans, as applicable.
- Ensuring that the clinical site has sufficient test articles and supplies.
- Clarifying questions regarding the study.
- Resolving study issues or problems that may arise.
- Reviewing of study records and source documentation verification in accordance with the monitoring plan.

18. ETHICAL AND REGULATORY ASPECTS

18.1. Study-Specific Design Considerations

Potential subjects will be fully informed of the risks and requirements of the study, and, during the study, subjects will be given any new information that may affect their decision to continue participation. Subjects will be told that their consent to participate in the study is voluntary and may be withdrawn at any time with no reason given and without penalty or loss of benefits to which they would otherwise be entitled. Subjects will only be enrolled if the subject is fully able to understand the risks, benefits, and potential adverse events of the study and provide their consent voluntarily.

18.2. Investigator Responsibility

The Principal Investigator is responsible for ensuring that the clinical study is performed in accordance with the signed agreement, the investigational plan, according to ISO 14155:2020¹ and applicable regulatory requirements. GCP is an international ethical and scientific quality standard for designing, conducting, recording, and reporting studies that involve the participation of human subjects. Compliance with this standard provides public assurance that the rights, safety, and well-being of study subjects are protected, consistent with the principles of the Declaration of Helsinki 64th WMA General Assembly 2013² and that the clinical study data are credible. The Investigator must maintain clinical study files in accordance with ISO 14155:2020¹ and applicable regulatory requirements.

18.3. Independent Ethics Committee or Institutional Review Board (IEC/IRB)

Before the start of the study, the Investigator (or Sponsor when applicable) will provide the IEC/IRB with current and complete copies of the following documents (where applicable):

- Final protocol.
- Sponsor-approved informed consent form (and any other written materials to be provided to the subjects).
- Investigator's Brochure (or equivalent information).
- Sponsor-approved subject recruitment materials.
- Information on compensation for study-related injuries or payment to subjects for participation in the study.
- Investigator's curriculum vitae, clinical licenses, or equivalent information (unless not required, as documented by IEC/IRB).
- Information regarding funding, name of the Sponsor, institutional affiliations, other potential conflicts of interest, and incentives for subjects.
- Any other documents that the IEC/IRB requests to fulfill its obligation.

This study will be undertaken only after IEC/IRB has given full approval of the final protocol, the informed consent form, applicable recruiting materials, and subject compensation programs, and the Sponsor has received a copy of this approval. This approval letter must be dated and must clearly identify the documents being approved.

During the study, the Investigator (or Sponsor when applicable) will send the following documents to the IEC/IRB for their review and approval, where appropriate:

- Protocol revisions
- Revision(s) to informed consent form and any other written materials to be provided to subjects
- If applicable, new or revised subject recruitment materials approved by the Sponsor
- Revisions to compensation for study-related injuries or payment to subjects for participation in the study
- Investigator's Brochure revisions
- Summaries of the status of the study (at least annually or at intervals stipulated in guidelines of the IEC/IRB)
- Reports of adverse events that are serious, unanticipated, and associated with the test articles, according to the IRB's requirements
- New information that may adversely affect the safety of the subjects or the conduct of the study
- Major protocol deviations as required by the IEC/IRB
- Report of deaths of subjects under the Investigator's care
- Notification if a new Investigator is responsible for the study at the clinical site
- Any other requirements of the IEC/IRB

For protocol revisions that increase subject risk, the revisions and applicable informed consent form revisions must be submitted promptly to the IEC/IRB for review and approval before implementation of the change(s).

At least once a year, the IEC/IRB will review and reapprove this clinical study. This request should be documented in writing.

At the end of the study, the Investigator (or Sponsor where required) will notify the IEC/IRB about the study completion. Documentation of this notification must be retained at the clinical site and a copy provided to the CRO or Sponsor as applicable.

